 - Healthy patients free of any medical condition.

Exclusion criteria:

- Patients with medical conditions that may affect periodontal healing or regeneration.
- Patients with a history of allergic reactions, pregnant or breastfeeding females,
 smokers and alcoholics
- Patients with current or previous drugs intake that may predispose to gingival enlargement.
- Patients under orthodontic treatment or had orthodontic treatment in the past six months.
- Carious teeth, proximal restorations or fixed prosthesis.
- Patients with a history of traumatic oral hygiene measures or periodontal surgeries over the last six months at the area of interest or having any scar tissue.
- Poor oral hygiene patients.

11. Interventions

11a-General operative procedure

- The patients who fulfil the inclusion criteria will be enrolled.
- The nature of the study will be explained to each patient as well as the importance of compliance with pre- and post-operative instructions and follow-up visits.
- Each patient will be asked to sign an informed consent (appendix 1)
- After enrolment, periodontal examination and full periodontal charts will be recorded for each patient including Papilla Class I1, CP-BC plaque Index (*Leary et al., 1967*), gingival bleeding Index (*Ainamo & Bay, 1975*), probing depth (PD), clinical attachment level (CAL) and gingival recession.

Radiographic Evaluation

Standardized digital periapical radiographs will be obtained preoperatively and at follow-up using the long cone paralleling technique. All radiographs will be obtained using the same equipment, film exposure and development conditions.

Pre-surgical therapy

- All patient will receive strict oral hygiene instructions full mouth supra and sub-gingival debridement using hand instruments and ultrasonic scalers under local anesthesia.
- Four to six weeks following pre-surgical therapy, a periodontal re-evaluation will be performed to confirm the suitability of the chosen sites for this periodontal surgical study.
- The clinical and radiographic parameters will be recorded at baseline

The patients will be randomly assigned into two groups: A total of 36 sites (18 site per group)

Group A (Intervention): Patients will receive Tube technique.

Group B (Control): Patients will receive Hyaluronic acid.

Surgical Procedures

Group A (Intervention): Patients will receive Tube technique (Hooshang et al. 2020).

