- 8) The size of the needle does not matter for this procedure; we use 4-0 silk with an FS2 cutting needle and a 4-0 chromic gut suture with a C-6 (FS-2) cutting needle.
- 9) Using the index finger and thumb the graft will be squeezed from both ends inward for at least 4 to 5 minutes to further stabilize the graft into position. Both patients are instructed to avoid

brushing or flossing the recipient as well as donor site. They are also asked to avoid hot, chewy, sticky foods. They were advised to ice the wound to reduce post-surgical swelling.

Group B (Control): Patients will receive Hyaluronic acid (HA) (0.1) mm (*Abdelraouf etal. 2019*) The product used in this trial is Restylane Lidocaine (Restylane-Lidocaine cross-linked Hyaluronic Acid Filler, Galderma S.A, Sweden). Restylane was the first FDA-approved HA filler in 2003. Restylane is a non-animal stabilised cross-linked HA filler with an HA concentration of 20 mg/ml. The longevity of Restylane filler in tissues is approximately 6 months. Restylane-Lidocaine (FDA approved in 2012) is a newer product of Restylane with 0.3% lidocaine incorporated into the syringe itself.

- -Stent will be performed and re evaluation
- -After 4 weeks, re-evaluation is performed, and the degree of papillary deficiency according to *Nordland and Tarnow* 1998 classification as well as plaque and gingival indices will be assessed for eligibility. Alginate impression is taken for the involved arch/arches for the construction of study casts and fabrication of customized stents. Only patients with deficient papilla sites fulfilling the inclusion criteria are recalled, scheduled for the 1st injection after 1 week and will sign the informed consent.

After 1 week 3 injection will be given at each papilla site

- -In the injection phase, 3 injections are given at each papilla site: at baseline, 3- and 6-weeks intervals. At the first injection visit, before attempting to inject, clinical measurement of the height of the black triangle is done by measuring the distance between the deficient papilla tip and contact area (PT-CP distance) to the nearest 0.5 mm (baseline). This will be done using a graduated periodontal probe and the fabricated customized stent for proper and standardized positioning of the probe at each measurement interval

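### The Group B procedure places an eligibility re-check and consent after the assignment sentence and in the control arm only, contradicting the common pre-allocation order given elsewhere in the protocol

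*Protocol*

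**What the plan says.** **The common order.** Protocol section 11a states "Each patient will be asked to sign an informed consent (appendix 1"), as part of enrolment. Under Pre-surgical therapy it continues: "Four to six weeks following pre-surgical therapy, a periodontal re-evaluation will be performed to confirm the suitability of the chosen sites". Baseline parameters are then recorded, and only after that comes the assignment sentence, "The patients will be randomly assigned into two groups: A total of 36 sites (18 site per group").

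**The timeline and allocation sections.** Section 13 marks the eligibility screen and informed consent at T0, and allocation and the intervention at T2. Section 16b has both groups prepared alike first, with the allocation decided afterwards from sealed envelopes.

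**The Group B order.** Under the Group B (Control) heading in section 11, after the assignment sentence, a re-evaluation after 4 weeks looks at the degree of papillary deficiency, "as well as plaque and gingival indices will be assessed for eligibility". Impressions for study casts and stents are taken. Then: "Only patients with deficient papilla sites fulfilling the inclusion criteria are recalled, scheduled for the 1st injection after 1 week". The end of that sentence adds that the recalled patients "will sign the informed consent".

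**Group A.** The Tube technique steps contain no eligibility check and no consent step.

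**The concern.** Consent has two positions that do not agree: at enrolment (sections 11a and 13), or after a re-check that appears only in the control text. Eligibility likewise is settled either before assignment for everyone, or again afterwards for controls alone.

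The stake is comparability of the arms. Anyone who followed the Group B paragraph literally could stop a control patient before the first injection for no longer meeting the criteria. They could also give that patient an opportunity to refuse with the arm already known, since section 17 says participants are not blinded. No Group A patient would face either step.

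The criterion is not neutral. The Nordland and Tarnow class, as described in the review of literature, is defined by where the papilla tip lies, and that is closely related to the area of the black triangle, the primary outcome.

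The loss could also be hard to repair later. The Group B follow-up visits and the area measurements in section 12 are counted from the first injection, so an allocated control who never reaches it has no defined measurement date.

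**Working it through.** **1. Passages side by side**

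| Step | Common text (sections 11a, 11 Pre-surgical therapy, 13, 16b) | Group B text |
|---|---|---|
| Consent | At enrolment, T0, all patients | After the 4-week re-check |
| Re-evaluation | 4 to 6 weeks after pre-surgical therapy, before assignment | After 4 weeks, starting event not given |
| Eligibility | Screened at T0; sites confirmed at re-evaluation | Assessed again; only those who qualify are recalled |
| Group A counterpart | Yes, same for all | None |

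No sentence identifies the Group B re-evaluation with the common one, and none says what happens to an assigned patient who fails it.

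**2. Timing check on which reading fits.** Section 13 gives T2 as a surgical phase of 8 weeks. The Group B text has 4 weeks to re-evaluation, 1 week to the first injection, and injections running to week 6.
- Re-check after allocation: 4 + 1 + 6 = 11 weeks, longer than T2.
- Re-check before allocation: 1 + 6 = 7 weeks, within T2.

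The timing favours a misplaced paragraph.

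**3. The plan's own sample size (sections 14 and 20).** With d = 1.32, two-sided alpha 0.05 and power 0.80, n = 2(1.960 + 0.842)² / 1.32² = 9.01, rounded up to 10 per group. The noncentral t calculation gives 10.07, with power 79.7% at 10 per group. The stated 10 is reproduced, and 10 × 1.2 = 12 gives the stated enrolment.

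**4. Possible shift in the control mean (illustration).** The SD of 0.74 mm2 and the target of 1 mm2 are from section 14. The removed fraction f and the correlation r between the screening variable and the outcome are assumptions; the documents give neither. If a fraction f is cut from one end of a normally distributed screening variable, the mean of those who remain moves by φ(z_f)/(1 − f) SD, and the outcome mean moves by r × 0.74 times that.

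| f | φ(z_f)/(1 − f) | r = 0.3 | r = 0.5 | r = 0.7 |
|---|---|---|---|---|
| 5% | 0.109 | 0.024 | 0.040 | 0.056 |
| 10% | 0.195 | 0.043 | 0.072 | 0.101 |
| 20% | 0.350 | 0.078 | 0.129 | 0.181 |

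Shifts are in mm2. The range is about 0.02 to 0.18, or 2% to 18% of the target difference.

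**5. Power with losses in Group B only (d = 1.32).**
- 12 v 12: 87.1%; 12 v 10: 83.4%; 12 v 8: 78.1%.
- Section 11 gives 18 per group instead of 12. On that count, 18 v 18: 97.0%; 18 v 14: 94.8%.

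The power loss is modest on either count.

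**The case against.** The strongest reply is that this is a paragraph in the wrong place, not a plan to filter one arm. The evidence for that is good:
- The timeline has consent and eligibility at T0, with no visit for either between allocation and injection.
- The 8-week T2 window fits a re-check before allocation and does not fit one after it.
- The 4 weeks in the Group B text has no starting event there; the only matching one is the common pre-surgical therapy.
- Group A step 3 also relies on a pre-surgical study model, so impressions look like a common step, although they are described only under Group B.
- The same Group B text pre-loads saline to blind patients. The trial has no saline arm, and section 17 rules out participant blinding. This suggests wording carried over from another study.

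This largely stands, and it limits what may be claimed. Three stronger readings are tempting and are not supported:
- A reader might infer that one-sided exclusion after randomisation is intended, or that Group B has a further re-evaluation on top of the common one. No sentence says either.
- A reader might infer that refusal with the arm known is part of the design. Sections 11a and 13 already require consent from everyone before assignment, so this needs consent to be deferred or taken twice.
- A reader might put the bias at up to a quarter of the target (0.350 × 0.74 = 0.26 mm2). That assumes 20% removal that perfectly truncates one tail of the six-month outcome. The documents support neither assumption, and the patients would already have passed the common re-evaluation.

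It is also fair that the sentence governs recall for injection and says nothing about who is analysed. What the reply does not do is remove the contradiction: the protocol never states that the two visits are the same.

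**Conclusion.** The point holds as an internal contradiction. The common sections place consent, eligibility and preparation before allocation; the Group B text places an eligibility condition and consent after it, for controls only. The likeliest explanation is a misplaced account of the common visit. Followed literally, the text would permit selection after allocation in one arm on a variable tied to the primary outcome.

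The size of any bias cannot be obtained from the documents. Under the assumed 5–20% removal and correlation of 0.3–0.7, with a normal model and SD 0.74 mm2, it is about 0.02–0.18 mm2 against the 1 mm2 target. Its direction cannot be fixed either, because the re-check combines papilla class with plaque and gingival indices. The case rests on comparability of the arms, not on power.

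**What to change.** Reconcile the passages:
1. Take the 4-week re-evaluation, eligibility confirmation, impressions and consent out of the Group B text. Put them in the common part of section 11 ahead of the assignment sentence, worded identically for both arms.
2. Keep one consent step, placed consistently with section 11a and the T0 entry in section 13.
3. State that no patient is removed for eligibility once the envelope has been opened.

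Which patients are analysed, and in which group, may be left to the statistical analysis plan.

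The cost is rewording, plus a formal amendment under section 25 if the protocol is already approved. No visit is added, because section 11 already contains the common re-evaluation.

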It is a minimally invasive non-surgical injection of hyaluronic acid that observed to overcome the major limiting factor in most surgical techniques regarding the limited blood supply and the small working space. Supported by a recent study conducted by *Jinng etal.* 2019, who reported significant increase in the height of the gingival papilla and reduction of the area of the black triangle between baseline and 3 or 6 months in a group with thick gingival biotype after injection with hyaluronic acid, that was adding possible maximum effect with minimal postoperative hazards.

II.B. Objectives of the study:

7. Aim of the study

The aim of this randomized clinical trial is to compare the clinical effect of surgical Tube technique versus Hyaluronic Acid gel injection in reconstruction of the interproximal papilla in patients with class II papillary defect.

Picots:

P: Population: patients with class II papillary defect.

I: Intervention: Tube technique hosting sub-epithelial connective tissue graft.

C: Control: Hyaluronic acid injection.

Primary outcome: interdental papilla loss (Decrease of black triangle) (mm2)

Secondary outcome: assessment of gain in papillary height, radiographic distance between (CP-

BC), assessment of CAL. PD reduction, amount of gingival recession.

T: Time frame: 6 months.

S: Study design: Randomized clinical trial.

Hypothesis:

Null hypothesis: There is no difference in the gain in papillary height comparing hyaluronic acid injection versus Tube technique in patients with class II papillary defect.

8.Trial design

The study is designed as a superiority, 2 arm parallel groups, randomized clinical trial with allocation ratio 1:1.

III. Methods

A) Participants, interventions and outcomes

9. Study settings:

This study will be carried out on patients enrolled from the outpatient and postgraduate clinics of Oral Medicine and Periodontology department, Faculty of Dentistry, Cairo University.

10. Eligibility criteria:

Inclusion Criteria:

- Highly motivated patients with papillary deficiency types II, according to *Nordland* and *Tarnow 1998* classification will be selected, having at least one deficient papilla in the anterior region.
- Distance between the contact point and inter-proximal bone crest (CP-BC) of ≤ 7 mm and probing depth of ≤ 4 mm at the deficient papillary site (*Abdelraouf etal. 2019*).
 - Patients with full mouth plaque index (PI) and gingival index (GI) scores should be between 0-1.

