- 1) Using a #15 blade, a semilunar incision is placed on the buccal aspect at the level of the mucogingival junction and a full-thickness flap was elevated. The flap is extended mesio-distally by an additional 4 to 5 mm than needed for the graft. This extension allowed the buccal flap to be freely moved into the recession area.
- 2) Another semilunar incision will be placed on the palatal aspect, such that the zenith of the

incision is located proximal to the alveolar crest.

- 3) An excavator (smaller than the width of the defect; evaluated pre-surgically on a study model) is used to carefully reflect the papilla away from the alveolar bone and root surfaces on the buccal aspect to access the interproximal region to prepare the bed for the graft. The excavator is used to do the same on the palatal aspect. The amount of reflection should yield a very relaxed papilla flap that permits placement of the papilla at the new coronal position without tension.
- 4) The recipient site at this time should resemble a "tube" with two openings; one on the buccal aspect at the mucogingival junction and one on the palatal aspect.
- 5) To harvest the graft, the incision is made parallel to and 2 mm away from the gingival margin. A thin flap containing the keratinized tissue is separated, then the second incision is made parallel to the gingival margin, but perpendicular to the alveolar bone. With a sharp periosteal elevator, the graft is raised with the periosteum and released at its anterior and posterior ends, and then from its base .The harvested graft should be larger than the side of interproximal defect in both cases: each graft will be 12 to 15 mm long, 5 mm wide, and 2 mm thick. A 4.0 chromic gut suture is used to pass the eye (swage) of the needle into the tube from the palate toward the buccal. The suture needle then engaged one end of the graft. An additional separate second suture is placed on the other end of the CT graft. One suture end (eye first) is passed through the tube toward the palatal side
- 6) The connective tissue graft is carefully slipped through the buccal aspect of the tube into the prepared interproximal bed towards the palate by means of the suture with the assistance of a periosteal elevator as needed. The thickest part of the graft is placed in the interproximal area.
- 7) The connective graft is sutured under the flaps onto the buccal and palatal tissues and the buccal and palatal flaps are sutured over the top of the graft.

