- Hyaluronic acid and saline are pre-loaded in insulin plastic syringes before injection for patient blinding. The needle is inserted 2-3 mm apical to the tip of the interdental papilla and directed coronally with an angulation of 45° to the long axis of the tooth, and the bevel directed apically. Then, the papilla is lightly moulded in an incisal direction for 1 minute using gauze.
- -In the follow-up phase, patients are recalled after 3,6months the first injection where clinical remeasurement of the black triangles and standardized digital clinical photographs will be retaken.

Postoperative care:

-Patient self-care instructions (Heitz et al. 2004):							
Avoid any hard brushing and trauma to the surgical site for two weeks.							
- Maintain a soft diet to avoid trauma to the surgical site.							
- After 24 hours patients can use warm saline rinses daily							
- Sutures will be removed fourteen days after the surgery.							
- Plaque control will be maintained by chlorohexidine mouth rinse after the surgery.							
12. Outcomes:							

Outcomes	Outcome name	Measuring device	Measuring units
1ry	interdental papilla loss	Photoshop CS5.	mm
outcome	(Decrease of black triangle		
	area) (mm2)		
2nd	Gain in papillary height	UNC Periodontal Probe	
outcomes			mm
	Change in the distance (CP-		
	BC)	Digital periapical radiograph	
		(linear measurement)	mm
	CAL		
		UNC Periodontal Probe	
	Pocket depth (PD)		mm
		UNC Periodontal probe	
	Gingival recession		mm
	(GR)	UNC Periodontal probe	
			mm
	Gingival bleeding		
		UNC Periodontal probe	G: : 1
			Gingival
	Plaque index		bleeding score
		UNC Periodontal probe	Diagna Inday
	Post-surgical patient		Plaque Index
	Satisfaction and post-	Post-surgical patient	score
	injection	satisfaction questionnaire	(1.7) noint 22-1-
		(PSPSQ) (Kiyak, Hohl, West,	(1-7) point scale
		& McNeill, 1984)	

-Digital clinical photographs: (SABT) mm (Abdelraouf et al. 2019)

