Gingival recession will be measured using UNC periodontal probe from the cemento-enamel junction till the gingival margin (Miller, 1985).

Gingival Bleeding score:

- Gingival bleeding score will be performed through gentle probing of the orifice of the gingival crevice from all four surfaces of all teeth using UNC Periodontal probe.
- Recorded as (+) if bleeding is present or (-) if bleeding is absent.
- If bleeding occurs within 10 seconds a positive finding is recorded and the number of positive sites is recorded and then expressed as a percentage of the number of sites examined (*Ainamo & Bay, 1975*).

Patient Satisfaction:

- Three questionnaires will be asked to determine patients' satisfaction with the outcome of surgery
 - 1. Considering this was an elective operation, how likely would you be to recommend it to others?
 - 2. If you had to make the decision again, how likely would you be to undergo this surgery'?
 - 3. Considering everything, how satisfied are you with the outcome of your surgery
- These questions could all be answered by the patient using a 7-point response scale where: Very Satisfied = 7; Not At All Satisfied = 1. (*Kiyak et al., 1984*).

13. Participant timeline

13.	T0	T1	T2	T3	T4	T5	1-
Participant			(Surgical	Starting	3-	6-	
timelineTime			phase- 8	from T2	months	months	
point			weeks)	till 7th	post-	post-	
				day	surgical	surgical	
Enrollment	X						
Eligibility	X						
screen							
Informed	X						
consent							
Initial phase		X					
(Oral hygiene							
measures)							
standardized							
periapical							
radiograph							
study casts	X					X	
Allocation			X				
Intervention							
Injection			X				
Surgical tube							
technique							
Post-operative				X			
Care							
Papillary		X	X		X	X	
height, CAL,							
PD, GR							
measurements							

SABT					
Patient		X		X	
Satisfaction					

14. Sample size:

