This power analysis used interdental papilla loss after six months as the primary outcome. Based upon the results of Awartani FA and Tatakis DN (2016), the mean and standard deviation (SD) for control group were 0.71 (0.74) mm2. The minimal clinically significant difference was 1 mm2according to expert opinion. Using alpha (α) level of (5%), β level of 0.8 (Power = 80%); the effect size for independent samples t-test (d) was 1.32 and the minimum estimated sample size was 10 sites per group. Sample size was increased to 12 sites per group to compensate for a drop-out rate of 20% after six months. Sample size calculation was performed using PS Power and Sample Size Calculations Version 3.

15. Recruitment strategy

- The main investigator will be responsible for recruitment of patients.
- Patients will be selected from the outpatient clinic of the Oral Medicine and Periodontology
 Department, Faculty of Dentistry Cairo University.
- Screening of patients will continue until the target sample is achieved.
- Identifying and recruiting potential subjects will be achieved through patient database.
- 1. One year.
- 2. Candidate self-funding

B) Assignment of interventions

16. Allocation

16a. Randomization

The patients will be randomly allocated to either the intervention group or the control group using computer generated random numbers that will be performed by the supervisor. The patients will be allocated in a ratio of 1:1.

16b. Allocation concealment mechanism

The two groups will be equally prepared for both surgical procedures. Then the decision of which group will receive Hyaluronic acid injection and which will Tube Technique will be taken according to the randomized numbers placed in opaque sealed envelopes. The number will be picked by the supervisor.

16c. Implementation

The supervisor will be responsible for generation of allocation sequence as will as assign the patients to the 2 intervention groups. The main investigator will be responsible for patient enrollment.

17. Masking/blinding:

Due to the type of intervention only the outcome assessor and the statistician will be blinded. Single blinded:

- Blinding of the participants is not applicable.
- Blinding of the operator is not applicable.
- Outcome assessor (primary and secondary outcomes) and biostatistician will be blinded.

Key elements of Random Sequence Generation in protocol are:

- 1-Method of random sequence generation (computerized random number generator).

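### Gingival bleeding is scored over the whole mouth, so a response at one treated papilla moves it by only about 2 percentage points

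*Protocol*

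**What the plan says.** The outcome table in Protocol Section 12 places gingival bleeding among the secondary outcomes. Under the Gingival Bleeding score heading, the probe is run along the "gingival crevice from all four surfaces of all teeth using UNC Periodontal probe". Each site is marked + or -, and "the number of positive sites is recorded and then expressed as a percentage of the number of sites examined". The result is one number per patient. No bleeding measure restricted to the treated papilla is defined.

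The rest of the design is local. Section 10 admits patients "having at least one deficient papilla in the anterior region", Section 11 applies the graft or the injections at the papilla, the primary outcome is the area of the black triangle at that site, and Section 14 counts the sample size in sites.

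Two further facts bear on the point. The Picots list in Section 7 does not name bleeding among the secondary outcomes. The timeline in Section 13 has no row for it, although it has one for papillary height, CAL, PD and GR.

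**The concern.** A local treatment is being judged by an average over the whole mouth. Nearly all of the denominator consists of surfaces that neither treatment touches, so a real difference in inflammation at the treated papilla is diluted to a small fraction of its size and set against variation in general hygiene between patients. A null result on this outcome would then say little about the treated site, yet could be read as showing that the two techniques leave equally healthy tissue there.

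This is an explicit outcome definition in the protocol, not a detail left for a later analysis plan. The site's own + or - reading is produced by the same examination, but the defined summary does not use it separately.

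**Working it through.** **The plan's own figures.** The protocol gives no SD, target difference or power for bleeding, so there is no bleeding figure to reproduce. Its only sample-size figure is for the primary outcome: d = 1.32, two-sided 5% (sidedness assumed) and 80% power give 10 per group by the normal approximation (11 by the exact t-test), in line with the stated 10. Section 14 raises this to 12 per group; Section 11 states 18 per group. Both are used below.

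**Step 1: largest shift from one papilla.** Surfaces examined = 4 × number of teeth. One papilla borders 2 proximal surfaces. Largest shift = 100 × 2 / (4 × teeth). The protocol gives no tooth count, so a range is assumed:

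| Teeth (assumed) | Surfaces | Largest shift |
|---|---|---|
| 20 | 80 | 2.50 points |
| 24 | 96 | 2.08 points |
| 28 | 112 | 1.79 points |
| 32 | 128 | 1.56 points |

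This is the extreme case: both surfaces bleed in every patient of one arm and in none of the other.

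**Step 2: power for that shift.** Two-sided 5% t-test, n per group, 2n − 2 degrees of freedom, noncentrality = (shift / SD) × √(n/2). Example: shift 1.79, SD 3 and n = 12 give 0.595 × 2.449 = 1.46 on 22 degrees of freedom, hence power 29%. The SDs are assumptions.

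| SD (points) | 12 per group | 18 per group |
|---|---|---|
| 2 | 55% | 74% |
| 3 | 29% | 41% |
| 5 | 13% | 18% |
| 10 | 7% | 8% |

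**Step 3: a less extreme local effect.** A 30-point difference in bleeding probability at the two surfaces shifts the score by 0.30 × 1.79 = 0.54 points. Power at 12 per group is 10% at SD 2, falling to 5% at SD 10.

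**Step 4: sensitivity to the number of surfaces (28 teeth, 12 per group).**
- Two separate papillae, 4 surfaces: 400/112 = 3.57 points; power 80% at SD 3, 39% at SD 5, 13% at SD 10.
- All 8 surfaces of both adjacent teeth: 800/112 = 7.14 points; power 92% at SD 5, 55% at SD 8, 39% at SD 10.

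**Step 5: the site reading instead.** With one + or - reading per patient and the same 30-point difference, Fisher's exact test at 12 per group has 21% to 28% power, depending on the lower proportion (28% for 0% versus 30%, 21% for 20% versus 50%). That is low, but well above the 5% to 10% in Step 3.

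**The case against.** The strongest reply is that the protocol never says the score is meant to capture inflammation at the papilla. It sits next to the plaque index, it is part of the full charting at enrolment, and eligibility is also judged on the whole mouth: "Patients with full mouth plaque index (PI) and gingival index (GI) scores should be between 0-1". On this view it is a hygiene index used as such, and a site score is a matter of preference. Part of this stands: the full-mouth percentage is a sound description of hygiene and should be kept. But the protocol lists it as an outcome in a comparison of two local treatments and gives no bleeding measure for the site.

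A reader might infer that the outcome cannot detect any treatment effect. The documents do not support that:
- Section 10 sets no maximum number of papillae.
- In Group A "The flap is extended mesio-distally by an additional 4 to 5 mm than needed for the graft", so more than two surfaces may respond. Step 4 shows how far this can change the power.
- A patient-level effect, for example through altered brushing or because "Plaque control will be maintained by chlorohexidine mouth rinse after the surgery", could also move a full-mouth score.
- Patients with poor hygiene are excluded and all receive debridement, so a small SD is plausible. At SD 2 the power is 55%, not negligible.

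A reader might also infer that the trial could not tell swollen from healthy tissue in the black triangle. That does not follow either. PD, CAL and GR are separate outcomes measured at baseline, 3 and 6 months, and swelling that moves the gingival margin would affect PD and GR. Nor does bleeding measure swelling volume.

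Finally, it may be said that the individual readings remain on the chart and could be analysed later. That is true, and it is why the fix is cheap, but the outcome as defined does not use them.

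**Conclusion.** The point holds as a minor one. As defined, the bleeding outcome dilutes a response at one treated papilla to at most about 2 percentage points (1.8 with 28 teeth; 1.6 to 2.5 for 32 down to 20 teeth). The ceiling rises to 3.6 points for two separate papillae and about 7 if every surface of both adjacent teeth responds. For one papilla, even the extreme contrast stays below 80% power at 12 or 18 per group over the SDs examined. The outcome is therefore a weak measure of the treated site and mainly a measure of oral hygiene.

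The sizes rest on assumed tooth counts and assumed SDs, since the protocol gives neither. The primary outcome, the sample size and the main conclusion of the trial are not affected.

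**What to change.** - In Section 12, define the between-arm bleeding outcome as the + or - reading at the two proximal surfaces bordering each treated papilla, taken from the same full-mouth probing. State how the two readings combine into one result per papilla.
- In Section 13, add a bleeding row at baseline, 3 and 6 months. Without it, it is only an inference that the readings are taken at follow-up.
- Keep the full-mouth percentage, labelled as a description of oral hygiene.

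The cost is a sentence or two in Section 12 and one timeline row. No new procedure is needed if the full-mouth probing is done at those visits. The downside is that a binary site outcome is coarse in a trial of this size (21% to 28% power for a 30-point difference at 12 per group), so it should be reported as supportive, with its confidence interval.
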